13.5 Interim Analyses for Efficacy

After the first 16 patients are followed up for one year, we will estimate the 1-year local progression free survival. If the upper bound of a two-sided 98% confidence interval (critical value alpha = 0.02) of local progression free survival does not exceed 30% in cohort A, or less than 50% in cohort B, the accrual at that cohort will be halted and trial will be re-evaluated.

13.6 Data Analysis

We will perform separate analyses for Cohorts A and B. Descriptive summary statistics (mean, median, standard deviation, range, or proportion) will be presented for demographic and clinical characteristics of patients or treated lesions.

Toxicity will be summarized by type and grade for each cohort. The rate of grade 3 or higher GI toxicity will be estimated along with its 95% CI. This study will evaluate the efficacy of fractionated Linac based SBRT based on local-regional progression free survival (LFSP). LPFS is defined as the elapsed time from the start date of Linac based SBRT treatment to the date of documented local/regional tumor progression or death, whichever occurs first. We will plot the Kaplan-Meier curve for LPFS and estimate 1-yr local control and its 95% confidence interval based on KM estimate and Greenwood's formula. In addition, we will consider death without local progression as a competing event, and estimate cumulative incidence rate of local-regional progression using a competing risk analysis.

Other outcomes to be studied in this group of patients include, overall survival (OS), progression free survival (PFS) and quality of life. OS is defined as the elapsed time from the start date of Linac based SBRT treatment to death due to any cause; PFS is the time from the start date of Linac based SBRT treatment to disease progression or death, whichever occurs first. OS and PFS will be summarized using Kaplan-Meier plot.

Quality of life will be assessed via EORTC QLQ-C30 (v3.0) questionnaires. Our study population is pancreatic cancer subjects, and the analysis will be focused on Global Health Status/QoL scale, symptom scale (fatigue, pain), and functional scale (physical functioning, role functioning, emotional functioning). For each module, summary statistics of the score will be reported as baseline and follow up time. Changes of quality of life score before and after treatment will be tested via paired t-test. In addition, mixture effect models will be fitted for accessing the quality of life changes over time. The frequency of patients who reach minimal clinically important difference of 10-points change from baseline will be tabulated by time. The time to definitive deterioration in quality of life will be analyzed using the Kaplan Meier method.

REFERENCES

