	STEREOTACTIC BODY RADIATION
	THERAPY (SBRT) FOR PALLIATIVE
	MANAGEMENT OF UNRESECTABLE
	RECURRENT OR RESIDUAL PANCREATIC
	OR PERIAMPULLARY ADENOCARCINOMA
STUDY PHASE	II
INDICATION	Unresectable recurrent or residual pancreatic or
	periampullary tumors
PRIMARY OBJECTIVE	• To evaluate rates of late (> 3 months after treatment) gastrointestinal toxicity following fractionated Linac based SBRT for pancreatic tumors. Toxicities of note include grade 2 or greater gastritis, enteritis, fistula, or ulcer and any other grade 3 or greater gastrointestinal toxicity.
SECONDARY OBJECTIVES	• To evaluate rates of acute (within 3 months of treatment) gastrointestinal toxicity following fractionated Linac based SBRT for pancreatic tumors. Toxicities of note include any grade 3 or greater gastrointestinal toxicity.
	• To evaluate local progression free survival, overall survival, metastasis-free survival, and progression-free survival rates following Linac based SBRT in patients with unresectable recurrent or residual pancreatic or periampullary adenocarcinoma.
	• To evaluate the ability of Linac based SBRT to provide pain control among symptomatic patients as measured by pain medication requirement at 3, 6 and 12 months after treatment.
	• To evaluate the utility of FDG-PET for treatment planning and estimation of progression-free survival.
	• To develop and standardize Linac based SBRT delivery and dosimetric parameters.
	• To evaluate toxicity and outcomes among two cohorts of patients: a) patients with recurrent or residual disease after previous chemoradiation therapy, with or without surgery, who will be treated with 5 Gy x 5 and (b) patients with recurrent or residual disease after chemotherapy only, (with or without surgery), who will be treated with 6.6 Gy x 5.
HYPOTHESES	No standard treatment option has yet been
	established for patients with recurrent or residual
	disease after definitive treatment of pancreatic or

	periampullary cancers (duodenal, ampullary, bile
	duct). Linac based stereotactic body radiation
	therapy (SBRT) administered in 1-3 fractions has
	been shown to be an effective treatment option for
	patients with unresectable, locally advanced
	pancreatic adenocarcinoma, achieving local control
	rates of 84-92% at one year. Associated late
	gastrointestinal toxicity rates have been reported to
	be 22-25% at 1 year. We hypothesize that similarly
	excellent local control rates (80-90% at one year)

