11.1.6 Progression-Free Survival (or other parameters)

The criteria for time to progression and progression-free survival (PFS) will be the duration from Linac based SBRT treatment to documented local/regional or distant progression or death. Local PFS will be measured as the duration from Linac based SBRT treatment to local progression or death from any cause.

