13.3 Plan of Analysis

Demographic and clinical characteristics of patients and the characteristics of treated lesions (volume, location, and modality) will be summarized by means, medians, standard deviations, ranges and proportions as applicable. Toxicities will be tabulated by type and grade at each follow-up interval. All adverse events will be reported to the SKCCC Data Safety Monitoring Committee and the JHH IRB. The study may be stopped before reaching the accrual goal at the recommendation of any of these groups. The level of progression free survival (and other categorical outcomes) will be tabulated at each follow-up interval. The percentage of individuals free from local progression will be computed with exact 95% confidence intervals. Time to event outcomes (overall survival, metastasis free survival, and progression free survival) will be summarized using Kaplan-Meier curves and medians with 95%

confidence intervals calculated using Greenwood's formula. A competing risks analysis of local progression at 6, 12, and 18 months will be conducted. The measurements of the volume of the pancreatic tumors based upon CT and/or PET-CT scans will be compared using paired t-tests or Wilcoxon signed-rank tests as appropriate. Quality of life at each interval will be calculated and compared using the recommended guidelines from the module (available by E-mail: [contact]). [name] from MD Anderson will also help with data analysis. Data will be transferred via secure JH Box and totally anonymized.

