The sample size is 60 patients per cohort. The primary outcome used to determine the sample size is the percentage of individuals with a late gastrointestinal toxicity (grade 2-4) at one year. The late grade 2 or greater toxicity rates was previously observed for other treatment regiments for locally advanced pancreatic cancer were approximately 40%. We hypothesize that in each cohort, the toxicity rate for this regimen will be 20%, a 50% reduction. The stopping rules for futility were calculated based upon a two-stage design with a total sample size of 60 and an interim analysis of 16 patients (note: accrual will continue while interim analysis is being conducted). Within 16 patients, if 7 or more patients have late grade 2 or greater gastritis, enteritis, fistula, ulcer, or late grade 3 or greater GI toxicity, the trial will be stopped. If 6 or fewer patients have late grade 2 or greater gastritis, enteritis, fistula, ulcer, or late grade 3 or greater GI toxicity, then the study will continue enrolling patients until 60 patients have been accrued. After 60 patients are enrolled, if 17 or more of the patients have late grade 2 or greater gastritis, enteritis, fistula, ulcer, or late grade 3 or greater GI toxicity, the null hypothesis will not be rejected. If 16 or fewer of the patients have late grade 2 or greater gastritis, enteritis, fistula, ulcer, or late grade 3 or greater GI toxicity, we will conclude that one year late toxicity is below 40%. This design will reach 91% power with 2% type I error for grade 2 or greater late toxicity, and the probability of early termination is 0.47. In addition, this sample size will reach 89% and 90% power to test the increase of 1-year local progression free survival from 30% to 45% in cohort A and 50% to 65% in cohort B, respectively.

The calculation is based on a one-sided test at significance level 0.04, assuming exponential distribution for local progression time and 2.5 year uniform accrual time with 1 year follow up.

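### Section 13.6 gives the name 1-year local control to a Kaplan-Meier value of LPFS that counts deaths; at the plan's own targets it reads 45% (A) and 65% (B) and does not estimate the control hypothesised at 80-90%

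*Combined protocol and SAP*

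**What the plan says.** Two sections define LPFS, and both count deaths. Section 11.1.6: "Local PFS will be measured as the duration from Linac based SBRT treatment to local progression or death from any cause". Section 13.6 ends the LPFS interval at the "date of documented local/regional tumor progression or death, whichever occurs first".

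The next step in 13.6 is: "We will plot the Kaplan-Meier curve for LPFS and estimate 1-yr local control and its 95% confidence interval based on KM estimate". No other Kaplan-Meier endpoint for local disease is defined there.

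The plan also provides other looks at local progression:
- Section 13.6 adds that "we will consider death without local progression as a competing event, and estimate cumulative incidence rate of local-regional progression".
- Section 13.3: "A competing risks analysis of local progression at 6, 12, and 18 months will be conducted".
- Section 13.3: "The percentage of individuals free from local progression will be computed with exact 95% confidence intervals". It does not say how a patient who dies without progression is counted.

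None of these three is named as the estimate of local control.

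On expected values, the Synopsis hypothesises "excellent local control rates (80-90% at one year", against 84-92% at one year cited from earlier work. Section 13.4.2 powers the trial "to test the increase of 1-year local progression free survival from 30% to 45% in cohort A and 50% to 65% in cohort B".

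**The concern.** A patient who dies with a controlled tumour is an event on the LPFS curve. Reading local control off that curve counts this patient as a local failure. In a population with high one-year mortality, such deaths could be most of the events.

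If 13.6 is followed as written, the report will carry a figure that includes deaths, with its confidence interval, under the name local control. The natural benchmarks for a figure with that name are the 80-90% hypothesis and the 84-92% cited in the Synopsis. A cohort that met its own LPFS target exactly would then appear to miss the local control hypothesis by a wide margin, although nothing had gone wrong.

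**Working it through.** **Inputs.** From 13.4.2: 60 patients per cohort; 1-year LPFS of 30% against 45% (A) and 50% against 65% (B); one-sided alpha 0.04; exponential times; 2.5 years of uniform accrual plus 1 year of follow-up; stated power 89% and 90%. From the Synopsis: local control 80-90%. From 3.3: a single-fraction series with 84% freedom from local progression and 21% overall survival (OS) at 12 months. The documents give neither 1-year OS nor the split between deaths and local progressions for this population, so both are treated as unknown below.

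**1. The plan's own figure.** With hazard λ = -ln(1-year LPFS), expected events are d = 60 × [1 - (exp(-λ) - exp(-3.5λ))/(2.5λ)], and power = Φ{[ln(λ0/λ1) - 1.751/√d0] × √d1}.
- A: d0 = 54.3, d1 = 48.3; power = Φ{[0.411 - 0.238] × 6.95} = 88.6%.
- B: d0 = 45.7, d1 = 36.1; power = Φ{[0.476 - 0.259] × 6.01} = 90.4%.

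These match the stated 89% and 90%. Simulation of a log-hazard test under the same assumptions gives 86.8% and 88.8%. So 45% and 65% are the 1-year values of the tested curve at target. The arithmetic cannot show that deaths are counted; the definitions in 11.1.6 and 13.6 do. The reference in 13.4.2 to an exponential local progression time is loose wording, since the quantity tested is named as LPFS.

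**2. What the labelled value would read.** At target it is 45% in A and 65% in B, whatever the mix of deaths and progressions. With no censoring before 12 months, Greenwood's formula reduces to p(1-p)/n:
- A: 0.45 ± 1.96 × √(0.45 × 0.55/60) = 0.324 to 0.576.
- B: 0.65 ± 1.96 × √(0.65 × 0.35/60) = 0.529 to 0.771.

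Both intervals lie below 80%.

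**3. How the documents use local control elsewhere.** In the single-fraction series, a rate that counted deaths could not exceed the 21% alive at 12 months. The 84% therefore did not count them.

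**4. Size of the gap, taking local control as one minus the cumulative incidence (1-CIF).** Let s be the share of first events by 1 year that are local progression. Then 1-CIF = 1 - s(1 - LPFS), and the gap to LPFS is (1 - s)(1 - LPFS).

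| s (assumed) | 1-CIF in A, LPFS 45% | 1-CIF in B, LPFS 65% |
|---|---|---|
| 10% | 94.5% | 96.5% |
| 25% | 86.3% | 91.3% |
| 50% | 72.5% | 82.5% |
| 100% | 45% | 65% |

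The labelled value equals 1-CIF only if nobody dies without prior local progression. A 1-CIF of 80-90% requires s = 0.10/0.55 to 0.20/0.55, about 18-36%, in A, and 0.10/0.35 to 0.20/0.35, about 29-57%, in B. The gap is then 80-90% minus 45%, or 35-45 points, in A, and 80-90% minus 65%, or 15-25 points, in B.

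**5. The same, taking 80-90% as cause-specific control under independent exponential hazards.** Here LPFS = control × OS, so the targets imply 1-year OS of 0.45/0.90 to 0.45/0.80 = 50-56% in A and 0.65/0.90 to 0.65/0.80 = 72-81% in B. With a = -ln(control) and d = -ln(OS), CIF = a/(a+d) × (1 - exp(-(a+d))).
- A: 1-CIF = 0.846 (control 80%) to 0.927 (control 90%); gap to 45% about 40-48 points.
- B: 1-CIF = 0.819 to 0.914; gap to 65% about 17-26 points.

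**The case against.** The best defence is that this is a slip of terminology. The definition of LPFS, deaths included, stands immediately before the sentence at issue, and the competing-risk analysis follows it. A report that follows 13.3 and 13.6 would show the LPFS curve, the cumulative incidence and OS together. Local control is not a listed endpoint, and no test or halt rule is tied to 80-90%. The sentence might also describe two outputs, an LPFS curve and a separate Kaplan-Meier estimate of local control.

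Much of this stands. The analysis needed is already in the plan, and no trial decision depends on the label. The size of the gap is illustrative, because the split of events is unknown.

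The two-output reading is strained, because 13.6 defines no second Kaplan-Meier endpoint from which local control could come. Nor does the neighbouring text cure the label: the competing-risk analysis is introduced as an addition, while the name local control and its confidence interval are attached to the other estimate. Local control is also part of the stated hypothesis, so readers can be expected to look for it.

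**Conclusion.** The concern holds as a wrongly labelled estimate. The value called 1-year local control is 1-year LPFS. It is capped by 1-year OS, reads 45% and 65% at the plan's targets, and cannot address the 80-90% hypothesis. The label, the cap and the two readings follow from the text alone. The confidence intervals assume 60 evaluable patients and no censoring before 12 months.

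The gap to local control needs an assumption. It is 35-45 points (A) and 15-25 points (B) if 80-90% is a 1-CIF value, or about 40-48 and 17-26 points if 80-90% is cause-specific control under independent exponential hazards.

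A reader might infer three stronger things that the documents do not support:
- That the trial could reach a wrong decision. The test and the halt rule are set on LPFS, the stated power reproduces, and the primary endpoint is toxicity.
- That the plan lacks a valid analysis of local control. It has one in 13.3 and 13.6, but does not give it that name.
- That the LPFS targets contradict the 80-90% hypothesis. They are different quantities and can both be true. For example, the 1-year survival of 50% that 3.2 reports in another population, with control of 80-90%, gives LPFS of 40-45% under independence.

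**What to change.** In 13.6:
1. Call the Kaplan-Meier value 1-year LPFS (progression or death).
2. Report local control from the competing-risk analysis already planned, as the 12-month cumulative incidence of local/regional progression, or one minus it, with a 95% CI. Show it beside 1-year OS, because it looks better as early deaths rise: with the formula in step 5 of the working, cause-specific control of 70% gives a 1-CIF of about 73% at 81% OS but 78% at 50% OS.
3. Do not set the LPFS value against the 80-90% hypothesis or the 84-92% figures. Keep any comparison of the competing-risk estimate with them descriptive. Note that the 84% did not count deaths, and that the 92% in 3.3 is a crude proportion (78 of 85 patients with response or stable disease lasting 3-36 months), not a 1-year time-to-event rate.

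The cost is a small amount of SAP wording. No new data or analysis is needed.

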3.3 Rationale for Use in Treatment of Locally Progressive or Recurrent Disease

The development of recurrent pancreatic cancer after definitive treatment with surgery, radiation, chemotherapy, or a combination of these universally portends a dismal prognosis, with the 5-year survival for such patients being 5.6% or less (45). Unfortunately, this scenario is not uncommon; even among the small number of patients (10-15%) able to undergo potentially curative surgical resection, more than 80% subsequently develop recurrent disease (46). Among the majority of patients with pancreatic cancer who present with unresectable disease, chemoradiation is able to transiently stabilize the disease in some patients and to prolong median survival to 8-14 months (47-50). However, virtually 100% of patients develop disease progression and succumb within 3 years (51-55).

The pattern of recurrence in pancreatic cancer is well known (11,18,56,57) and is similar to that of periampullary adenocarcinoma (35). Following resection, 71-77% develop distant metastases within 2 years, often accompanied by concurrent locoregional recurrence, while up to 30% (58, 59) exhibit isolated locoregional recurrence (60,61). Patients who develop combined distant/locoregional recurrence have a median survival of 3 months from the time

of recurrence, while those with isolated locoregional recurrence have a median survival of 7 months (60). Locoregional recurrence is, therefore, a common and serious problem both in the setting of metastatic disease and as an isolated entity. Symptomatic manifestations include pain, gastric outlet/small bowel obstruction, portal hypertension, biliary obstruction, and malnutrition (61). Although survival is determined chiefly by systemic disease control, local control is an important factor contributing to quality of life (62,63). The symptoms associated with local recurrence require a mode of treatment that is swift and efficacious in order to restore patient quality of life and give patients the best chance at greater overall survival.

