Two recent studies support this assertion. In 2009, Chang *et al.* reported on the use of Linac based SBRT delivered as 25 Gy in a single fraction for patients with unresectable pancreatic adenocarcinoma (67). Of the 77 patients, 58% had locally advanced disease and 14% had medically inoperable disease, but the remainder were similar to our population in that they had either low-burden metastatic disease (19%) or locally recurrent disease (8%). Results were encouraging, with rates of freedom from local progression at 6 and 12 months of 91% and 84%, respectively. Overall survival at 6 and 12 months was 56% and 21%, respectively. Only 5% of patients experienced grade 2 or greater acute toxicity, 4% experienced grade 2 late toxicity, and 9% experienced grade 3 or greater late toxicity. Rates of grade 2 or greater late toxicity were 11% and 25% at 6 and 12 months, respectively.

In 2010, Didolkar *et al.* reported on the use of Linac based SBRT doses ranging from 15 to 30 Gy delivered in 3 equal fractions, with mean dose of 25.5 Gy over 3 days (66). Eighty-five patients were studied; the majority (71 patients) had locally advanced disease, but a small number (14 patients) were included who were similar to our population in that they had locally recurrent disease. Results were again encouraging, with 78 patients (92%) achieving complete response, partial response, or stable disease for a duration of 3-36 months with a

median of 8 months. Pain relief was noted in the vast majority of patients lasting for 18-24 weeks. Median survival from time of Linac based SBRT was 8.65 months, which is comparable to or better than reported results for locally advanced pancreatic cancer (69-72). Nineteen patients (22.4%) developed grade 3-4 gastrointestinal toxicity, consisting of duodenitis, gastritis, and diarrhea in order of decreasing frequency. One patient developed renal failure.

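### Section 13.6 does not say how deaths and missing forms enter the quality-of-life analyses, so change scores at later visits describe survivors only and can understate decline

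*Combined protocol and SAP*

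**What the plan says.** Quality of life before and after SBRT is a secondary endpoint (section 13.1.2). Forms are due at baseline, 4-6 weeks, and 4, 6, 9 and 12 months, and then at each later follow-up visit (sections 6.1.5 and 10).

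Besides descriptive scores by visit, section 13.6 plans four analyses:

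- A test of change: "Changes of quality of life score before and after treatment will be tested via paired t-test". No visit is named.
- A longitudinal model: "In addition, mixture effect models will be fitted for accessing the quality of life changes over time". No missing-data assumption or sensitivity analysis is given.
- A responder table: "The frequency of patients who reach minimal clinically important difference of 10-points change from baseline will be tabulated by time". It states neither the direction of change nor the denominator.
- A time-to-event analysis: "The time to definitive deterioration in quality of life will be analyzed using the Kaplan Meier method". Definitive deterioration is not defined, and death is not mentioned.

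For other outcomes the same section is explicit. Death is an event in LPFS and PFS, and for local-regional progression it says: "In addition, we will consider death without local progression as a competing event". Section 13.3 refers to the questionnaire module's guidelines for calculating and comparing scores, but states no rule for deaths or missing forms.

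**The concern.** A paired test needs a baseline score and a follow-up score, so only patients who are alive and return the form contribute. In this disease death removes a large share of each cohort within a year. If the patients who decline most also die soonest, the mean change among those remaining is better than the course of the treated group, and the gap grows with each visit.

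The trial's title gives palliation as its purpose, and section 3.2 predicts no adverse effect on quality of life. Survivor selection pushes in the direction of that prediction. Section 3.2 also plans a comparison with historical chemoradiation cohorts, where a difference in mortality alone could shift survivor-only means.

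The time-to-deterioration curve has a separate problem. Until the role of death is fixed, the same data can yield very different percentages.

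**Working it through.** **Plan's own figure.** The documents give no power, SD or expected completion rate for quality of life, so there is nothing to reproduce. The design figure used is "The sample size is 60 patients per cohort".

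**Step 1: patients alive at 12 months, out of 60.** The cited series states: "Overall survival at 6 and 12 months was 56% and 21%, respectively". Section 3.3 also reports that patients with "isolated locoregional recurrence have a median survival of 7" months, counted from recurrence. Medians are converted as S(12) = 0.5^(12/median), which assumes exponential survival.

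| Source | 12-month figure | Alive of 60 |
|---|---|---|
| Single-fraction series, 3.3 | 21% | 60 x 0.21 = 12.6 |
| Median 7 months, 3.3 | 0.5^(12/7) = 30.5% | 18.3 |
| Median 8.65 months, 3-fraction series, 3.3 | 0.5^(12/8.65) = 38.2% | 22.9 |
| Gemcitabine plus 25 Gy study, 3.2 | 50% | 30 |
| Cohort A LPFS target, 13.4.2 | 45% | at least 27 |
| Cohort B LPFS target, 13.4.2 | 65% | at least 39 |

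The last two rows are floors. LPFS counts death, so overall survival cannot be lower than LPFS. The working range is therefore about 13 to 39, before any unreturned forms. At 6 months the single-fraction series gives 60 x 0.56 = 33.6.

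**Step 2: mean change among survivors.** All inputs here are assumptions: 12-month change C = -10 + 15u with u standard normal, and death hazard h0 x HR^(-u), with h0 set so that mean survival matches the stated OS. The -10 equals the plan's 10-point threshold. Survivor mean = -10 + 15 x E[u S(u)] / E[S(u)]. Numerical integration gives:

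| Hazard per SD of worse change | OS 21% | OS 30% | OS 50% | OS 65% |
|---|---|---|---|---|
| x1 (no link) | -10 | -10 | -10 | -10 |
| x1.25 | -5.0 | -6.1 | -7.7 | -8.6 |
| x1.5 | -1.5 | -3.3 | -6.0 | -7.5 |
| x2 | +2.3 | -0.1 | -3.8 | -6.0 |

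Simulation of the x1.5 row agrees to within 0.2 (-1.7 at 21%, -6.1 at 50%, -7.5 at 65%).

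**Step 3: does the planned mixed model cure it?** This is a separate simulation with 60 patients, a 7-month median survival, a mean slope of -1.5 points per month (so -18 at 12 months), slope SD 1.5, the planned visits, and correlation rho between slope and survival (120 simulated trials per row).

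| rho | Paired change, survivors | Mixed model, 12 x slope |
|---|---|---|
| 0 | -17.8 | -17.9 |
| 0.3 | -12.0 | -14.3 |
| 0.5 | -7.6 | -10.7 |
| 0.7 | -3.2 | -7.8 |

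The mixed model recovers part of the loss, not all of it.

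**Step 4: time to deterioration.** Assume 30% net deterioration at 12 months, exponential and independent of death. Then lq = -ln(0.70)/12 = 0.0297 and, for a 7-month median, ld = ln(2)/7 = 0.0990.

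- Deaths censored, 1-KM: 30%.
- Cumulative incidence, death competing: lq/(lq+ld) x [1 - exp(-12(lq+ld))] = 0.231 x 0.787 = 18%.
- Deterioration or death: 1 - exp(-12(lq+ld)) = 79%.

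With a median of 8.65 months the last two become 20% and 73%. Starting from 50% net, the three figures are 50%, 31-34% and 81-85%.

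**The case against.** The strongest reply is that this is a gap in specification, not an analysis shown to be biased. Much of that stands.

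- **A reader might infer that a real decline will be reported as stable.** The documents do not support that. With no link between quality of life and survival there is no bias. In the x1.5 model the chance of a significant decline is still 50% with 27 survivors, 62% with 30 and 88% with 39. Masking needs low survival or a strong link, and no document gives the strength of the link.
- **A reader might infer that the plan ignores death or censors it.** The section is silent. Kaplan-Meier does not imply censoring at death, since the same section uses it for LPFS and PFS with death as an event.
- **A reader might infer that the Kaplan-Meier curve flatters the treatment.** Censoring deaths overstates deterioration against cumulative incidence. It understates it only against deterioration-or-death.
- **A reader might take the low survival figures as a ceiling.** The 21% series included 19% metastatic patients, who are excluded here, and the LPFS targets imply at least 27 and 39 alive.
- **Mitigation exists.** Mixed-effects models use all observed scores. Questionnaires are mailed to patients too ill to travel (6.4) and may be returned by mail or email (section 10). These help with non-response among the living. They do not say how death counts.

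A change score among patients alive and responding is also a legitimate summary. The all-patient mean in steps 2 and 3 includes hypothetical scores after death. What remains is that the plan neither labels the summary in that way nor shows how many patients lie behind it.

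**Conclusion.** The point holds as a gap in specification with a plausible direction of bias for the change scores. As written, paired change at later visits applies only to patients alive and responding, about 13 to 39 of 60 per cohort at 12 months depending on which figure in the documents is used. If worse quality of life goes with earlier death, decline is understated: under the x1.5 assumption a 10-point fall reads as about -1.5, -6.0 or -7.5 at 21%, 50% or 65% survival. The true change, SD and hazard ratio are assumptions, and with no link the bias is zero. For time to deterioration the finding is ambiguity, not a known direction: an assumed 30% could equally be presented as 18-20% or 73-79%. Quality of life is a secondary endpoint with no decision rule attached, so this is a cheap improvement and not a threat to the primary conclusion.

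**What to change.** In section 13.6:

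1. Define definitive deterioration as a first worsening of at least 10 points from baseline without later recovery, stating for each scale which direction is worse. Report both deterioration-or-death by Kaplan-Meier and the cumulative incidence of deterioration with death as a competing event.
2. At each visit, tabulate all treated patients as improved by at least 10 points, stable, worsened by at least 10 points, died, or alive without a form.
3. Make the mixed-effects model the main analysis of change over time. Label paired tests at later visits as applying to patients alive and responding. Add a sensitivity analysis for dropout due to death, such as a joint or pattern-mixture model.

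Confining paired tests to the 4-6 week visit, or splitting each cohort by time of death, is a matter of preference and is not needed; with 60 patients such strata would be small.

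Cost: SAP wording and some extra programming, with no new data. The reported figures may look less favourable.
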